### Method

**Intervention.** The tooth brushing intervention was developed in conjunction with dental hygienist researchers and consistent with American Dental Hygienist Association recommendations. It has been deployed successfully in our previous projects, including the large RCT conducted as the initial project of R01 NR007652 (see Preliminary study 1), and is described fully in the publication of the project's primary findings. In the initial project, 229 subjects were randomly assigned to tooth brushing, and the intervention was provided three times daily. In the proposed project, subjects will be randomized to receive tooth brushing once, twice, or three times a day.

In brief, we will systematically brush all tooth surfaces, gums, and tongue with a soft pediatric toothbrush, using dry mouth toothpaste, for two minutes per intervention; length of the intervention will be measured using a timer. The tooth surfaces will be brushed using a gentle vibrating, back and forth, rolling motion, beginning with buccal surfaces, proceeding to lingual surfaces, and concluding with biting surfaces, for 5 strokes on each tooth surface. In areas of the mouth where teeth are missing, the intervention provider will brush the gums. Then, the tongue will be brushed. If the subject is unresponsive and/or has clenched the mouth shut, we will use a mouth prop to gently open the mouth. Following tooth brushing, the mouth will be rinsed with alcohol-free mouthwash and oral fluids will be removed by suctioning the

mouth with an oral suction tip. Moisturizing gel will be gently applied to the oral mucus membranes. The complete intervention requires approximately 15 minutes.

We have found that soft pediatric toothbrushes are more easily maneuverable in the mouths of endotracheally intubated subjects and enables removal of plaque without disturbing oral tubes. Soft bristles reduce potential for trauma and bleeding, and in our previous studies were not associated with adverse effects such as damage to mucosa which can result from hard bristled toothbrushes. We considered use of an electric toothbrush, but selected the manual toothbrush for two primary reasons. First, electric toothbrushes have been associated with significantly increased risk of transient bacteremia compared to manual toothbrushes in healthy populations. Second, electric toothbrushes have been tested in two VAP trials, and outcomes were no better than trials in which manual toothbrushes were used (neither manual nor electric toothbrushes have been shown to reduce VAP risk). Furthermore, the additional cost of an electric toothbrush as a standard of care will hinder broad adoption of the study findings to clinical practice settings.

We have also chosen not to use disposable toothbrushes. We reason that requirement for a disposable toothbrush will reduce translation to practice related to increased cost. Further, we recently examined environmental contamination of toothbrushes in the ICU (F31NR012340, Fellow: [name]). While 14 of 100 toothbrushes became contaminated with potential pathogenic organisms over 24 to 72 hours of use, there was a significant association between tooth brush contamination and the use of a storage container ( $p$ -value = 0.01), regardless of whether the toothbrush was reused for 24, 48, or 72 hours. Thus, our intervention will include rinsing the toothbrush well after use, and storage in a dry well ventilated space apart from other patient care items (a condition in which none of the toothbrushes studied became contaminated).

## Key Variables and Measurement

In this final phase of our investigation of oral care in mechanically ventilated adults, our goal is to determine optimal tooth brushing frequency. Taken as a whole, the work conducted in R01 NR007652 (the proposed project combined with the results of the previous and current projects) results in clear, complete, evidence-based guidance for nurses providing oral care to mechanically ventilated adults.

The primary aims of the proposed project are: 1) Evaluate the clinical equivalence (non-inferiority) of three tooth brushing frequencies on oral health (dental plaque and mucosal inflammation) in critically ill adults receiving mechanical ventilation; and 2) Quantify and compare the safety of three tooth brushing frequencies on serious adverse outcomes, including ventilator associated complications and clinically relevant HAIs (including VAP, bacteremia, and sepsis). A secondary aim is to investigate patient factors that influence tooth brushing frequency benefit and risk in critically ill adults.

We will accomplish these objectives using a prospective, randomized, experimental design. Subjects (n=345) will be randomly assigned within 36 hours of intubation to one of three intervention groups which differ in frequency of tooth brushing (once, twice, or three times daily). The intervention, a standardized tooth brushing protocol developed and tested in the previous project, will be delivered by study personnel for 7 days, or until extubated (if extubation occurs within the first 7 days). Key variables and their measurement intervals are presented in Table 1, and will be described more fully in the Research Design section.

Table 1: Key variables

Concept	Variable	Measurement interval
Oral Health (Specific Aim 1)	Dental Plaque: UM-OHI, augmented with DPIA	Daily for 7 days while intubated, days 1,3,5 post-extubation*
	Gingival inflammation: GCF IL-1 $\beta$	Daily for 7 days while intubated, days 1,3,5 post-extubation*
Serious outcomes (Specific Aim 2)	Systemic Inflammatory Response Syndrome criteria	Daily for 7 days while intubated, days 1,3,5 post-extubation*
	HAI: positive epidemiologic surveillance report for VAE (including VAP), bacteremia, sepsis	Daily for 7 days while intubated, days 1,3,5 post-extubation*
	Length of stay (ICU and hospital)	Calculated at hospital discharge
	Length of intubation	Calculated at time of extubation
Patient factors (Specific Aim 3)	Demographics (age, gender, smoking status)	On study admission
	Severity of Illness: APACHE	On study admission
	Global oral health: DMFT	On study admission

\*Post-extubation data will not be collected on subjects who remain intubated beyond the 7 day intervention period.

**Oral Health: Dental Plaque.** Dental plaque will be assessed using the University of Mississippi Oral Hygiene Index (UM-OHI), with observations documented and augmented by use of a digital intraoral camera (obtaining images of every tooth at each observation for later analysis). The UM-OHI assessed prior to the first tooth brushing intervention, and daily every day for the first seven days of intubation. If extubated during the 7 day intervention period of the study, the UM-OHI will also be assessed following extubation on days 1,3 and 5 post-extubation to document resolution or persistence of dental plaque after resumption of self-administered oral hygiene. We will use dental hygienists to train study personnel to obtain the digital images, and as plaque assessors.

The UM-OHI assesses every tooth, and divides each tooth into more sections than standard tools used in dental practice, thus enhancing the ability to quantify plaque. The UM-OHI divides the oral cavity into 12 regions: left and right posterior teeth and anterior teeth in each arch, further subdivided into buccal (cheek side) and lingual (tongue side). Each tooth is divided into 5 sections for the buccal surface and 5 sections for the lingual surface. The 5 sections include the mesial, distal and middle sections (which is further subdivided horizontally into gingival, middle and occlusal sections). Each section (total of 10 for each tooth) is scored for the presence or absence of plaque. If plaque definitely exists in the section, it is scored a 1; if no plaque is present, the section receives a 0. Thus, each tooth is scored from 0 (no plaque) to 10 (plaque in every section). The mean plaque score for the subject is then calculated by dividing the total score by number of teeth.

In the initial project, plaque assessors who were blinded to group assignment visually scored dental plaque using the UM-OHI in real time at the bedside. In the proposed project, we will obtain digital images of all teeth (buccal and lingual) using an intraoral camera, and plaque assessors will visually score blinded images downloaded to a computer in the research office at a later date. Digital Plaque Image Analysis (DPIA) has been used to assess dental plaque in studies of dentifrices and other oral hygiene products. Bellamy and colleagues developed a DPIA system which captures images of healthy subjects' teeth via an external digital computer-controlled camera under white light without disclosing agents, as well as image processing and image analysis software that identifies color differences indicative of dental plaque. DPIA systems used in dental research (and designed for healthy subjects) will not serve our purpose, because they require a cooperative subject, sitting upright, and positioned in a cephalometric head restraint apparatus in order to obtain external images. However, intraoral cameras are now available, and these small portable handheld units (appearing similar to a digital oral thermometer with a camera positioned at the tip of the probe) are able to capture images of buccal and lingual tooth surfaces in white light outside a dental laboratory setting.

While the plaque assessment procedures used in our previous project worked sufficiently, we believe that documenting the condition of the teeth using an intraoral camera, in conjunction with plaque assessors applying UM-OHI assessment to those images, will provide several important advantages. Digital images of subjects' teeth provide documented, archival raw data which can be scored by multiple plaque assessors as needed to enhance both reliability and inter-rater reliability. Positioning the camera in the oral cavity will provide better visualization of the lingual surfaces of teeth, particularly teeth in proximity of the endotracheal tube, than direct external observation; this will enhance detection of plaque on surfaces which are difficult to directly observe. Intraoral imaging can be done more quickly than full bedside assessment, reducing any subject discomfort during the assessment. Conducting the UM-OHI scoring in the research office rather than at the bedside enhances blinding of the assessment. These procedures will also make the most efficient use of plaque assessor expertise.

**Oral Health: Oral Mucosal Inflammation.** We will quantify mucosal inflammation by determination of GCF IL-1 $\beta$ . Collection GCF is a well-developed dental research methodology dating to the 1960s, and has elements common to our expertise in collection of saliva and quantification of salivary biomarkers. GCF samples will be obtained prior to the first tooth brushing intervention, and daily every day for the first seven days of intubation. If extubated during the 7 day intervention period of the study, GCF samples will also be obtained on days 1,3 and 5 post-extubation to document resolution or persistence of inflammation after resumption of self-administered oral hygiene. Periopaper strips will be placed into the gingival margins of the maxillary premolars for thirty seconds; if these teeth are not present, the next adjacent teeth will be used. Using published methods, samples will be placed in PBS-BSA transport medium and frozen at -70°C until assay, when the GCF analytes will be eluted from the paper strips and assayed in duplicate for IL-1 $\beta$  using a commercial enzyme-linked immunosorbent assay (ELISA) system according to the manufacturer's instructions.

**Serious Outcomes: SIRS, VAE and HAIs.** We will obtain data from the subject's medical record to evaluate SIRS criteria (heart rate > 90, respiratory rate > 20 or PaCO2 < 32 mm Hg, WBC > 12,000 mm^3 or < 4000 mm^3 or > 10% bands, temperature > 38 °C or < 36 °C) prior to the first tooth brushing intervention and daily thereafter while tooth brushing interventions continue. We will also monitor the results of any blood cultures obtained for clinical purposes from our subjects during the study period in order to identify clinical bacteremia. TGH has a robust surveillance program for

identification of bacteremia, VAC (including VAP), and sepsis. We will obtain HAI surveillance data regarding all study subjects from the Hospital Epidemiologist, as well as collecting data from each subject's medical record regarding diagnoses of these conditions by the clinical providers. We will also calculate length of intubation and length of stay for all subjects.

Sample Description and Patient Factors. Data will be collected from the medical record on additional factors in order to provide a comprehensive description of the study sample and conduct an exploration of the influence of individual-level factors on tooth brushing benefit and risk. Demographic data will be collected on study admission, and include age, gender, race, ethnicity, and smoking status. Preexisting global oral health will be measured by DMFT (Decayed, Missing, and Filled Tooth) Index assessed at study admission. The DMFT is a classic instrument which is widely used in dental practice and research. The score is calculated by visually inspecting each tooth and adding the number of decayed teeth, absent teeth, and filled teeth. Scores can range from a score of 0 (all teeth present and without caries) to a score of 32 (every tooth evidencing dental disease through loss, active dental caries, or repaired dental disease). The summative score will be used in examination of the exploratory aim. Severity of illness will be documented on admission to the study using the Acute Physiology, Age, and Chronic Health Evaluation (APACHE III). The APACHE III total score may range from 0 to 299 and consists of the following sub-scores: vital sign/lab, pH/pCO2, neurological, age, and chronic health. Scoring is done using the worst values for the first ICU day.

The APACHE III will be used to describe the study population, to document the initial level of illness severity between the intervention groups, and explore the individual-level variables that may affect tooth brushing benefit and risk.

Additional data to describe the sample will include: reason for admission to the unit; administration of antibiotics prior to entry into the study; type of intubation (emergent, oral vs. nasal); daily ventilatory support data (ventilator mode, rate, type of support, positive end-expiratory pressure, pressure support ventilation, FiO2, PaO2, and SaO2) and daily enteral nutrition data (presence, route, rate, type of enteral nutrition, and highest daily gastric pH); and presence of antibiotic, histamine blocker, proton pump inhibitors, antacid, and vasopressor therapy during the study period.

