**6. Risk Reduction: Oral Care, Bacteremia, and Critical Care.** In a companion project to the initial R01 funding period (F31 NR009596, Fellow: [name]), the goals were to determine (1) the incidence of transient bacteremia related to tooth brushing in mechanically ventilated critically ill adults; (2) the relationship of oral microbial cultures and dental plaque scores to the incidence of transient bacteremia, clinical outcomes, and indicators of infection; and (3) the relationships among patient characteristics and clinical outcomes. All subjects (n=30) received a tooth brushing intervention twice daily for up to 48 hours. Three blood samples (before tooth brushing, 1 minute after the tooth brushing intervention, and 30 minutes after the intervention) for quantitative culture (lysis filtration) were collected at the first and last scheduled interventions. Five subjects (17%) had positive oral cultures for organisms other than normal oral flora (including *S. pneumoniae*, *coagulase-negative Staphylococcus*, *E. coli*, *S. aureus*, and *P. aeruginosa*) before the first tooth brushing intervention. None of the 30 subjects had evidence of transient bacteremia by positive quantitative blood cultures before or after the tooth brushing interventions. Patient characteristics were not statistically significant predictors for systemic inflammatory response syndrome, length of hospital stay, or length of intubation. In this small sample, dental plaque, DMFT and APACHE score were not found by logistic regression to be independent predictors of SIRS (likelihood ratio chi-square = .79,  $P = .85$ ). Despite the small sample size and limited length of data collection, this project provided

the opportunity to explore tooth brushing risk factors which we will further investigate in the proposed larger project, with a longer planned intervention period and post-extubation follow up.

Taken together, the preliminary studies presented in this application provide a substantial foundation for the proposed work, and clearly point to the examination of the frequency of tooth brushing as the final critical step in developing the evidence base for oral care in mechanically ventilated patients. Further, the preliminary studies document our expertise in the content relevant to and methodologies of the proposed project.

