
Once the subject has been enrolled, the Project Director will assign the subject to one of the three groups using a randomization schedule generated by [name]. A set of sequenced, sealed opaque envelopes will be prepared, each containing the assignment of an individual subject. At the time of enrollment, the Project Director will open the next envelope and proceed accordingly. [name] and the Data Manager will each keep a master copy of the randomization assignment.

Intervention and data collection procedures. Following obtainment of informed consent from the subject or LAR, subjects will be randomly assigned within 36 hours of intubation to one of three intervention groups which differ in frequency of tooth brushing (once, twice, or three times daily). The intervention, a standardized tooth brushing protocol developed and tested in the previous project, will be delivered by study personnel for 7 days, or until the subject is extubated if extubation occurs within the first 7 days.

Daily saliva periopaper GCF samples will be collected and digital images of teeth will be taken and identified only by the subject's arbitrary study number, not by any identifiable private information. GCF samples will be frozen at  $-70$  degrees in the Tampa General Hospital Office of Clinical Research Laboratory, and later transported to the

Biobehavioral Laboratory at the USF CON, and stored securely in the locked, limited access laboratory. Digital images of teeth will be obtained at close range such that photos will not include subject facial features.

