Data will be obtained from the patient's medical record, from assessment of the subject's mouth, and from biologic fluids (gingival crevicular fluid, GCF, collected on filter paper). On study admission, the following data will be collected: demographic data (age, gender, smoking status, reason for admission), severity of illness data (APACHE information), and a count of decayed, missing and filled teeth (DMFT). The following data will be collected every day through the first seven days of mechanical ventilation, or until extubated if extubation occurs within the first seven days: digital photos of all teeth (for use in UM-OHI dental plaque assessment), a sample of GCF collected on Periopaper (for GCF IL-1 $\beta$  assay), Systemic Inflammatory Response Syndrome criteria from the medical record, positive epidemiologic surveillance reports for enrolled subjects for VAE (including VAP), bacteremia, and sepsis from the TGH Epidemiology Department records. For subjects who are extubated during the first 7 days of mechanical ventilation, the same data collected during the study intervention period will also be collected after extubation on days 1,3,5 after extubation. Data regarding length of intubation, length of ICU stay and length of hospital stay will also be calculated from the medical record.

All data, including digital photos, will be collected on laptops in the clinical setting; these laptops will remain in the possession of study personnel at all times (unless locked in a cabinet in the locked research office), and all study-related files will be password protected. At the conclusion of each subject's participation, that subject's data will be transferred from the laptop computer to a secure, password protected file on the USF Health server, under the direct supervision of [name], with access limited to study personnel. Study information obtained will be kept strictly confidential, and it will not be possible to identify any participant from the reports that may result from this research.

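### Infection follow-up has no common window: five days after the last brushing for subjects extubated by day 7, none for those still intubated

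*Combined protocol and SAP*

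**What the plan says.** In Key Variables and Measurement, Table 1 defines the safety variable as "HAI: positive epidemiologic surveillance report for VAE (including VAP), bacteremia, sepsis" and schedules it "Daily for 7 days while intubated, days 1,3,5 post-extubation". The footnote to that schedule adds: "Post-extubation data will not be collected on subjects who remain intubated beyond the 7 day intervention period".

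The Procedures section agrees. Data, including the epidemiology reports, are collected "every day through the first seven days of mechanical ventilation, or until extubated if extubation occurs within the first seven days". For subjects extubated in that period, "the same data collected during the study intervention period will also be collected after extubation on days 1,3,5 after extubation". Section IX (Design) and Section XVI (A, Description; C, Research Material) give the same schedule. Brushing is delivered "for 7 days, or until the subject is extubated if extubation occurs within the first 7 days".

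The paragraph on serious outcomes in Key Variables and Measurement is less specific: "We will obtain HAI surveillance data regarding all study subjects from the Hospital Epidemiologist", together with chart diagnoses. It states no start or end of the window.

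In Section XI, Specific Aim 2 uses these data twice: as a proportion of subjects with HAI in each arm, with a 95% confidence interval, and as an incidence rate over person-days counted from intubation. The rate feeds the number needed to harm (NNH). Neither is tied to a common observation window.

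**The concern.** The length of time for which a subject can be seen to have an HAI depends on when that subject is extubated. Extubation happens after randomisation, and Table 1 lists length of intubation among the Aim 2 outcomes, so the plan itself allows that brushing frequency might affect it.

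The schedule leaves out the post-exposure period for the subjects with the longest exposure. The protocol's proposed harm is that organisms dislodged by brushing are aspirated or enter the bloodstream, and an infection started by the last brushings may be recognised some days later. The preliminary-studies section presents the present trial as an advance for studying brushing risk, "with a longer planned intervention period and post-extubation follow up", yet subjects ventilated beyond day 7 get no such follow-up.

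The reason given for the post-extubation visits is to see whether plaque and inflammation resolve once subjects clean their own teeth. That explains the plaque and gingival-fluid schedule. It gives no reason to end record-based infection surveillance at day 7 in subjects who are still in hospital.

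**Working it through.** **The plan's own figures.** The plan has no figure for the HAI windows. Its nearby figures reproduce and are not in dispute.
- Sample size: 2 × (1.2816 + 1.6449)² / 0.50² = 68.5, so 69 per group. Then 3 × 69 = 207 and 207 / 0.60 = 345, or 115 randomised per arm.
- Precision example: an exact binomial interval at 0.05 × 69 = 3.45 events gives 0.012 to 0.131, matching 0.01 to 0.13.

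**Windows implied by Table 1, its footnote and Procedures.** For extubation on day d (1 to 7), brushing ends on day d and the last HAI observation is day d + 5. The maximum number of brushings is d, 2d or 3d by arm.

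| Extubated | Last HAI observation | Days after last brushing | Maximum brushings (1/2/3 daily) |
|---|---|---|---|
| Day 1 | Day 6 | 5 | 1 / 2 / 3 |
| Day 2 | Day 7 | 5 | 2 / 4 / 6 |
| Day 4 | Day 9 | 5 | 4 / 8 / 12 |
| Day 7 | Day 12 | 5 | 7 / 14 / 21 |
| After day 7 | Day 7 | 0 | 7 / 14 / 21 |

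The last two rows have the same exposure but differ by five days of follow-up. Total observation in the last row is not the shortest: day-1 and day-2 extubations end at day 6 and day 7. The gap is in time after exposure.

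**Effect on the two Aim 2 measures.** The proportion divides events by subjects with no allowance for window length. The incidence rate allows for length, but events after day 7 in the ventilated group never enter its numerator. Its denominator is also unclear. If time from intubation were counted to day 12 for subjects observed only to day 7, their rate would be understated by a factor of 7/12 = 0.58.

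**Illustration of the loss (assumptions, not in the documents).** Let f be the share still intubated after day 7 and r their daily HAI hazard relative to the others. Let extubation be spread evenly over days 1 to 7, so that mean observation in that group is 9 days. Compare the present schedule with one giving everyone five days after brushing:

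missed share = 5fr / (5fr + 7fr + 9(1 − f))

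- f = 0.10, r = 1: 0.5 / (0.5 + 0.7 + 8.1) = 0.5 / 9.3 = 5%
- f = 0.40, r = 3: 6.0 / (6.0 + 8.4 + 5.4) = 6.0 / 19.8 = 30%

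The person-time added would be 115 × f × 5, or about 58 to 230 person-days per arm. The width of this range shows that the size depends on quantities the documents do not give.

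**Does a small loss change the NNH category?** The formula is NNH = 1 / (IR_n − IR_1), with rates per person-day. At 115 per arm and 6 to 12 days each, an arm has 690 to 1,380 person-days.
- A two-event difference gives 690/2 = 345 to 1,380/2 = 690, well above 100.
- Falling below 100 needs an excess of more than 690/100 = 6.9 to 1,380/100 = 13.8 events, that is 7 to 14. At the plan's illustrative 5%, an arm would expect 0.05 × 115 = 5.75.

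**The case against.** Four arguments can be made for leaving the schedule alone.

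1. *Surveillance data are promised for all subjects.* This is true, and longer capture may be what the investigators intend. But that paragraph states no window, while Table 1 and Procedures do, so it does not override them. The passages need to be reconciled.

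2. *The Table 2 decision rule uses person-day rates, not crude proportions.* This stands as far as unequal time is concerned. It does not recover events that were never observed, nor settle which days count.

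3. *The footnote applies identically to all three arms.* This stands. A reader might infer that the schedule biases the comparison between frequencies. The documents do not show that; it would require frequency to change ventilation duration or HAI timing.

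4. *Ending observation with assigned brushing avoids dilution.* After day 7, oral care for ventilated subjects returns to the bedside nurse, and the protocol describes that care as highly variable. The cost is real, but the argument has little force here because extubated subjects are already followed for five days off the intervention.

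A reader might also infer that one or two missed events per arm would move the NNH by a row of Table 2. That follows only if NNH is computed per subject (115/1 = 115, 115/2 = 57.5), a reading that the plan's remark about 100 individuals may invite. Under the person-day formula actually stated, it does not hold. Equal numbers lost in each arm would also leave the event difference unchanged. An equal proportional loss would shrink a real difference, but by a share the documents do not supply.

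**Conclusion.** The point holds as a matter of ascertainment. As scheduled, subjects extubated by day 7 have five days of HAI follow-up after their last brushing, and those still intubated have none, despite having as many brushings as anyone in their arm. Late HAIs in that group go uncaptured, and the crude proportions mix windows ending anywhere from day 6 to day 12.

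That much follows directly from the schedule. The rest is conditional. Calling the ventilated group the highest-risk is a reasonable inference, but the documents give no HAI rate by ventilation duration; only longest exposure follows from the design. No size can be derived from the documents, and the 5% to 30% range rests wholly on the stated assumptions. Between-arm bias is possible but not shown. The sample size and the Aim 1 plaque analysis are unaffected.

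**What to change.** Ascertain HAI over one fixed window for every randomised subject, for example through day 12, and state whether the clock starts at intubation or at randomisation, since the two can differ by up to 36 hours. Take the events from the epidemiology reports and medical records already obtained. Use the same window for the proportions and the person-day denominators, and say how death or discharge before its end is handled.

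Align Table 1 and its footnote, the serious-outcomes paragraph and the Procedures text. In doing so, reconcile the SIRS schedule, which that paragraph limits to the brushing period while Table 1 continues it after extubation. Leave the bedside plaque and gingival-fluid schedule unchanged.

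The cost is a few more days of record abstraction; records are already followed to discharge for length of stay. The added days fall under unassigned oral care and may dilute the contrast, as the post-extubation days already do. An analysis restricted to the assigned-brushing period can be reported as a sensitivity analysis.
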